7.2 Secondary Outcome Data

Other patient level data will be obtained for this study through retrospective chart review utilizing StarPanel and the RD. Data to be collected include:

- Demographics (e.g., age, sex, race)
- Hospitalizations (date of admission, date of discharge, hospital unit), hospice referrals, and time to hospice placement
- Days alive outside of hospital
- Discharges to hospice
- Date of death (where applicable)
- Clinical interventions, procedures, and events (e.g., surgeries, resuscitation, intubation, ventilator use) extracted from the charts will inform our analyses as to whether initially established palliative care goals of care were met. Examples of met goals could include DNR and advanced care directives being met and whether aggressive treatment has been pursued at the end of life, against the documented wishes of the patient.
- Physical symptoms (e.g., ascites, variceal bleeding, encephalopathy, delirium)
- Liver transplant status (deferred, listed, decline), MELD score, and number of completed liver transplants

Additional secondary outcome data include change of health-related quality of life, as measured by the Chronic Liver Disease Questionnaire (CLDQ),²⁹ change in general quality of life, patient mood, and patient and caregiver satisfaction with care across the study period. Demographic information will also be collected at baseline for all participants and caregivers. Participating hepatology staff will complete a brief survey to provide feedback and gauge satisfaction with intervention procedures.

Questionnaire data will be captured electronically via online REDCap survey or via paper copy. All participants (patient and caregivers in both usual care and intervention arms) will complete outcome measures at the same frequency – at Baseline, 4 weeks, and at 3, 6, 9, and 12-months post randomization. Baseline measures will be completed using a provided computer tablet, or paper version if preferred, on the inpatient hospital unit. If participant discharges from hospital prior to completion of questionnaires, and at the subsequent time points, participants (caregivers and patients) will complete assessments over the telephone with the study coordinator administering the questionnaires and documenting participant response on the REDCap survey form, or participants will complete assessments at home by accessing the REDCap survey form online directly. If the patient or caregiver prefers to complete assessments online or is unable to be reached by telephone, the study coordinator will provide the participant with instructions to access the online survey via email reminder with the link to the survey. Study Coordinator will attempt to contact the participant for completion of assessments up to 7 days post scheduled time-point. If unsuccessful after 7 days or if the participant prefers, paper versions of the assessments for the participant (patient or caregiver) and a stamped addressed envelope to return the completed assessments will be mailed.

If the patient returns to hospital and is inpatient at a scheduled assessment time point, the SC will meet with the patient or caregiver in-person to complete the assessments on the hospital unit by using a provided computer tablet or paper versions. See **Table 2** for the schedule of outcome assessments. If the study

participant dies while active in the study, a one-time, one-item survey will be completed by the caregiver 3 months after the death of the participant to gauge quality of death and dying.

Table 2

Schedule of Assessments						
Instrument	Baseline	Month 1 (Wk 4)*	Month 3 (Wk 13)*	Month 6 (Wk 26)*	Month 9 (Wk 39)*	Month 12 (Wk 52)*
Study Participant						
Demographic survey	X					
CLDQ	X	X	X	X	X	X
EQ-5D-5L	X	X	X	X	X	X
PROMIS Depression 4a	X	X	X	X	X	X
PROMIS Anxiety 4a	X	X	X	X	X	X
Quality of End-of-Life Care: Patient Questionnaire**	X	X	X	X	X	X
Caregiver						
Demographic survey	X					
Quality of End-of-Life Care: Caregiver Questionnaire**	X	X	X	X	X	X
Kingston Caregiver Stress Scale (KCSS)	X	X	X	X	X	X
QODD-1***						X***

* Call window for completing assessments is within 7 days after time-point. After 7 days, paper versions will be mailed.

** Survey renamed "Satisfaction Questionnaire"

*** Completed once, 3 months post-death of participant

Outcome data will be collected via:

Quality of Life Instruments

The Chronic Liver Disease Questionnaire (CLDQ)²⁹ is a 29-item self-report questionnaire addressing domains specific to patients with liver disease including: abdominal symptoms, fatigue, systemic symptoms, activity, emotional function, and worry. Items are scored on a Likert-type scale measuring frequency of symptoms within the timeframe of the 'last two weeks,' from 1 – All of the time to 7 – None of the time. Initially validated in adults with a variety of types and stages of liver disease, the CLDQ has shown the ability to detect differences between patients without cirrhosis, with early cirrhosis, and with advanced cirrhosis (based on Child's Pugh classification), has shown good concurrent validity when compared to clinical evidence of deterioration²⁹, and has the ability to detect significant improvement in health-related QOL between patients pre-liver transplant and post-transplant.³⁰ (**Appendix L**)

In addition to a liver disease-specific assessment, the EQ-5D-5L³¹ will be collected as a secondary outcome measurement. The EQ-5D-5L is a valid and reliable generic health survey questionnaire, with 5 items measuring dimensions of Mobility, Self-Care, Usual Activities, Pain/Discomfort, and Anxiety/Depression. The 5L version has 5 response categories ranging from absence of symptom to extreme experience of the symptom. The EQ-5D-5L has been evaluated in patients with chronic hepatic diseases and has shown good criterion-related and construct validity in liver transplant patients.³² Scalone et al. (2013) evaluated the 5L version compared to the 3L version in 1,088 adult patients with chronic hepatitis (HCV and HBV), cirrhosis, hepatic carcinoma, or a recent liver transplantation, finding the 5L version performed well with a reduction

in ceiling effect with a modest-low gain in discriminant validity and slightly higher convergent validity as compared to the 3L version.³³ (**Appendix M**)

Mood Instruments

We will use PROMIS adult short forms to assess mood in study participants, specifically depression (**Appendix N**) and anxiety (**Appendix O**). Patient Reported Outcomes Measurement Information System (PROMIS) is a system of highly reliable, validated, precise measures of patient-reported health status for physical, mental, and social well-being.³⁴ PROMIS' measures can be used as primary or secondary endpoints in clinical studies of the effectiveness of treatment. The domains of depression and anxiety are measured through four targeted questions each on a 5-point Likert scale. The four items are selected from a full item bank to yield an accurate estimate at a targeted range of the measured domain. Evaluation of construct validity has been accomplished through the specification and testing of hypotheses about the relationship between the PROMIS domain scores, actual clinical status, and other relevant variables. A variety of statistical techniques have been employed to evaluate these hypotheses including mixed-effects models, regression analysis, and structural equation models. Evaluation of construct validity is based on the relationship between the PROMIS scores and other health and clinical measures, and by evaluating known groups' validity.

Hospital Utilization

Days admitted as an inpatient will be compared between the usual care and intervention arm. Admission date, discharge date, and length of stay for inpatient hospitalizations and ICU admissions will be obtained from the Research Derivative. Associated costs and days alive outside of hospital will also be compared between arms.

Survival

Survival rates will be compared between the control and intervention arm one year after study enrollment.

Physical Symptoms

Disease trajectory including diagnoses and physical symptoms (e.g., ascites, variceal bleeding, encephalopathy) will be compared across arms.

Liver Transplant Status

Listing of liver transplant status (deferred, listed, declined), change in MELD score, and the number of completed liver transplants will be compared across arms.

Satisfaction Instruments

Quality of End-of-Life Care: Questionnaire for Patient, developed at the University of Washington was modified for the current study.³⁵ The original instrument is an 11-item self-report questionnaire designed for the patient to rate the clinician, doctor, or nurse practitioner on 11 elements measuring quality of care. Items are scored on a 10-point Likert-type scale with 0 = "Poor", 5 = "Very Good", and 10 = "Absolutely Perfect" with an option for Does Not Apply (NA). The study team has modified this original questionnaire to remove the "End-of-Life Care" title from the header (**Appendix P**).

Caregiver Instruments

The Quality of End-of-Life Care: Questionnaire for Patient was modified for use by the Caregiver. The study team modified questions to be applicable for caregiver rather than patient response. For example, altering item 2 from "Responsive to your emotional needs . . ." to "Responsive to the patient's emotional needs . . .". The study team has modified this original questionnaire to remove the "End-of-Life Care" title from the header (**Appendix Q**).

If patients die during study participation, caregivers will be asked to complete one questionnaire at 3-months post-death to gauge quality of end-of-life care. The Quality of Death and Dying (QODD-1) is a 1-item questionnaire that measures overall quality of dying with the question, “Overall, how would you rate the quality of your loved one’s dying?” Response options range from 0 – a “terrible” experience to 10 – an “almost perfect” experience. The QODD-1 has shown to correlate significantly with clinical variables associated with end-of-life care and palliative care.^{36,37} (**Appendix R**)

The Kingston Caregiver Stress Scale (KCSS)³⁸ will be used to measure caregiver stress. The KCSS is designed to measure stress experienced by lay caregivers, not institutional staff, and was designed to monitor change in an individual's stress over time. Ten items are grouped into three categories: care giving, family, and financial issues. (**Appendix S**)

Provider satisfaction

Study hepatologists will be surveyed once prior to research participant enrollment and again every 6 months after the first participant is enrolled until study close-out, to gauge level of satisfaction with the palliative care service. An important part of the feasibility of a large-scale palliative care program is provider satisfaction. The “ICU Provider Satisfaction Survey with the Palliative Care Program: Veterans Affairs of Ann Arbor” instrument is available online and has been modified for the current study by removing the ‘ICU’ reference and revising ‘pain’ to symptoms more relevant to the current population. (**Appendix T**)

7.3 Process Outcomes

Concordance with plan will be measured via EMR derived, standardized, objective and measurable variables including CPR, mechanical ventilation, intubation, feeding tubes, re-admission, medications, etc. Although each intervention encounter will ultimately be tailored to fit the individual’s specific needs, structured protocols will be in place to insure all participants receive consistent palliative care services and that those services are properly documented and recorded. All standard components of the clinical intervention listed above will be assessed and recorded by the palliative care and/or research staff. The palliative care provider will enter data elements into structured fields on a standardized palliative care Starform, and the research staff will enter relevant data elements into a REDCap database.

8.0 Statistical Analyses

Power Calculations

Power calculation was conducted on the primary outcome (time to first hospital readmission) using Cox proportional hazards model accounting for competing risk of death.³⁹ Assuming 50% 1-year mortality in both arms of the expected study cohort (‘surprise question’ inclusion which is comparable to a 50% 1-year mortality rate), with type I error of 0.05 and power of 80%, the minimum detectable hazard ratio (HR) under sample size N=400 was calculated given varying hospital readmission rate in the usual care arm ranging from 0.5 to 0.9. The corresponding rate reduction in the intervention arm (DR) and the relative rate reduction (RDR) were also provided. See **Table 3**. To assess clinical rationale of the power calculation, 1-year hospital readmission rate was assessed from pilot data obtained from a retrospective data pull via the Research Derivative. Admission to a study hepatologist during a 3-month window was required for cohort inclusion, and subsequent admission data (1-year post ‘qualifying admission’) was analyzed. Of the 151 patients included in the pilot data, 93 patients (62%) were readmitted within 1 year of the qualifying admission with a 1-year mortality rate of 35%. This pilot cohort (35% mortality rate) may be healthier than expected study cohort. However, due to competing risk of death, we are not sure whether the 1-year readmission rate of 62% from the pilot cohort is an overestimate or underestimate of the target population. Nonetheless, the proposed sample size provides sufficient power (80%) to detect rate reduction

of 13% when the hospital readmission rate in the usual care arm is between 50% and 70%, which is comparable with the pilot data.

Table 3

Various risk of readmission in the usual care arm (R), and the corresponding minimum detectable hazard ratio (HR) and the corresponding inverse HR (1/HR), difference of risk of readmission (DR) and relative difference of the first readmission (RDR) under sample sizes N = 400 with power 80% and type I error 0.05.

N = 400				
R	HR	1/HR	DR	RDR
50%	0.67	1.5	13%	0.26
60%	0.69	1.4	13%	0.22
70%	0.71	1.4	13%	0.18
80%	0.73	1.4	11%	0.14
90%	0.74	1.4	8.3%	0.092

Analyses Plan

Demographic and clinical characteristics of the participants such as age, gender, etc. will be compared between the control and the intervention arms using Wilcoxon rank-sum test for continuous variables and Pearson's Chi-square for categorical variables.

Aim 1: Time to first hospital readmission within 1-year post randomization will be compared across treatment assignment using Cox proportional hazards model, accounting for the competing risk of death and adjusting for relevant demographic and clinical characteristics. A less than 1 hazard ratio for the treatment group status implies reduced readmission rates in the intervention arm given equal mortality rates.

Aim 2: Days alive out of hospital within 6-months post randomization, total days in hospital and ICU within 1-year post randomization, number and cost of hospital admissions within 1-year post randomization, median length of stay per admission, number of transfers to hospice within 1-year post randomization, time to hospice placement after referral, survival, presence of advance directives within 1-year post randomization, presence of physical symptoms, transplant status listing (deferred, listed, declined), and number of completed liver transplants will be obtained via chart review and compared across treatment assignment using proportional odds model for ordinal outcomes, Cox proportional hazards model for time-to-event outcome and logistic regression for binary outcomes, adjusting for relevant demographic and clinical characteristics.

Aims 3 and 4: Both cross-sectional and longitudinal analysis will be conducted to compare between group differences in CLDQ. For the cross-sectional study, for each time point of data collection, linear regression with ordinary least square will be used with CLDQ as the dependent variable (DV) and treatment assignment (0 for control arm and 1 for the intervention arm) as the independent variable (IV) of interest adjusting for baseline CLDQ and potential confounding factors based on clinical and statistical considerations. A positive value of the regression parameter for treatment status indicates higher CLDQ in the intervention arm. For longitudinal analysis, linear mixed model will be adopted including follow-up time and the interaction between follow-up time and treatment group on top of the cross-sectional model. The interaction term is included to compare decreasing rate of CLDQ between groups with a positive value of the corresponding regression parameter indicating slower decline rate of CLDQ in the intervention arm.

The same series of analyses for the CLDQ will be conducted for the PROMIS (depression, anxiety), ED-5D-5L, the Quality of End-of-Life Care patient and caregiver questionnaires, and the KCSS. Histogram of baseline secondary outcomes will be used to evaluate ceiling/flooring effect and degree of skewedness. Appropriate transformation such as log transformation will be considered for highly skewed secondary outcomes to improve efficiency. A positive value of the main effect for intervention status in the cross-sectional analyses and a positive value of the interaction effect in the longitudinal analyses indicate favorable intervention effect.

Aim 5: Summary descriptive measures such as mean, quartiles and standard deviation for continuous variables and frequencies for categorical variables will be provided for process outcomes from participants in the intervention arm to evaluate fidelity of the proposed intervention and generalizability of implementing a large-scale intervention program. The following data will be collected for each arm: percentage of patients with answered surprise question (stratified by provider), percentage of patients with a 'No' response to the surprise question (stratified by provider), percentage of patients with 'No' response to the surprise question who were approved for study enrollment (stratified by provider), percentage of intervention patients who received initial PC inpatient consult, percentage of patients who received scheduled follow-up telephone contact, percentage of patients who attended an appointment for care after referral was obtained, percentage of patients with completed questionnaires at each time point, percentage of patients who received Palliative Care materials, and percentage of patients who received an inpatient PC consultation upon hospital readmission during the intervention phase will be calculated.

Interim Analysis

Interim analysis will be conducted when N=30 and N=150 participants are enrolled and followed for at least 6 months to evaluate whether the study is feasible, study procedures are conducted as intended, and that there is not significant patient dropout for mortality or other reasons.

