5.0 Participant Selection

Approximately 400 adult hepatology patients with poor prognosis (identified by the ‘surprise question’ see below) will be randomized to receive either usual hepatic care (control group, N=200) or usual hepatic care with comprehensive palliative care services (intervention group, N=200). Any Vanderbilt patient admitted to the primary inpatient service of one of the study hepatologists with limited life expectancy may be eligible for participation. We expect a participation rate of ~75% (based on the participation rate of a similar study conducted by [name]), and no more than 10% of patients excluded based on eligibility criteria. We are powered to detect a 13% difference in readmission rate between treatment arms with 400 participants, assuming equal mortality across arms (see section 8.0, Statistical Analyses). As this is an internally funded study, we will have flexibility to enroll patients past the the accrual goal of 24-months in order to enroll 400 participants if necessary.

Inclusion Criteria:

- Inpatient at Vanderbilt University Medical Center with advanced liver disease, whose treating hepatologist indicates a ‘No’ response to the question, “Would you be surprised if this patient died within 1 year?”

Exclusion Criteria:

- Age < 18 years
- Inability to give written informed consent (patient or surrogate decision-maker)
- Inability to respond to questions in English
- Treating hepatologist denies permission to enroll
- Receiving hepatology care at non-Vanderbilt sites (to ensure appropriate follow-up)

Recruitment

Potential patients will be identified within StarPanel using hepatology service codes and/or attending physician name. Patients’ electronic medical records will be manually reviewed by study personnel to confirm preliminary eligibility. Once preliminary eligibility is established, the treating hepatologist will receive a prompt via email with a REDCap survey link to respond to the question, “Would you be surprised if this patient died within 1 year?” The ‘surprise question’ has been used in a variety of patient populations for prognosis and to evaluate appropriateness for palliative care^{25,26} and has shown specificity (69.3%) and

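### Table 3 counts too many events: at its own hazard ratios, N=400 gives about 75–78% power, not 80%, when usual-care readmission is 50–70%

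*Combined protocol and SAP*

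**What the plan says.** Section 8.0 (Power Calculations) bases the sample size on time to first readmission within one year, "using Cox proportional hazards model accounting for competing risk of death", "with type I error of 0.05 and power of 80"%. It fixes N and solves for the effect: "the minimum detectable hazard ratio (HR) under sample size N=400 was calculated given varying hospital readmission rate in the usual care arm", for rates from 50% to 90%. Table 3 lists, for each usual-care risk R, the hazard ratio (HR), the absolute difference in readmission risk (DR) and the relative difference (RDR). The text concludes "Nonetheless, the proposed sample size provides sufficient power (80%) to detect rate reduction" of 13% for R between 50% and 70%, and calls this range comparable with the 62% seen in the pilot data.

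Section 5.0 gives the allocation as "usual hepatic care (control group, N=200") and "usual hepatic care with comprehensive palliative care services (intervention group, N=200"). It repeats the claim without the range: "We are powered to detect a 13% difference in readmission rate between treatment arms with 400 participants", subject to equal mortality.

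Neither section states the event fraction used, whether the test is one- or two-sided, or any allowance for loss.

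**The concern.** Power for a hazard ratio depends on the number of events in the two arms together. If the intervention lowers readmission, the intervention arm contributes fewer events than usual care. Table 3 shows that reduction in its DR column, but its HR column looks as if the reduction was left out of the event count. That overstates events and therefore power.

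The 80% power and the 13-point difference are the plan's stated justification for 400 participants. If the design does not deliver them, a null result would be read against a sensitivity the trial never had.

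**Working it through.** **Inputs.** N = 400, 200 per arm (Section 5.0). Type I error 0.05, power 80%, and the R, HR, DR and RDR columns (Section 8.0, Table 3). Two-sided testing is assumed; a one-sided test does not reproduce the table (step 3). No loss is applied.

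**1. What the table assumes for the intervention arm.** Under proportional hazards on the cumulative-incidence scale, the intervention-arm risk is R₂ = 1 − (1 − R)^HR. For the first row, R₂ = 1 − 0.5^0.67 = 0.371, so R − R₂ = 12.9 points. Across the five rows R − R₂ is 12.9, 13.1, 12.5, 10.9 and 8.2 points, against printed values of 13, 13, 13, 11 and 8.3. The table therefore assumes fewer intervention-arm readmissions: 37% against 50% in row 1.

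**2. Events the tabulated HRs need.** Events for 80% power = 4(1.96 + 0.8416)² / ln(HR)². For HR 0.67 this is 31.4 / 0.1604 = 196.

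| R | HR | Events needed | Needed / 400 | As a multiple of R |
|---|---|---|---|---|
| 50% | 0.67 | 196 | 0.489 | 0.98 |
| 60% | 0.69 | 228 | 0.570 | 0.95 |
| 70% | 0.71 | 268 | 0.669 | 0.96 |
| 80% | 0.73 | 317 | 0.793 | 0.99 |
| 90% | 0.74 | 346 | 0.866 | 0.96 |

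The implied event fraction is 0.95 to 0.99 of the usual-care risk, close to applying R to both arms.

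**3. Reproducing the plan's figures.** Minimum detectable HR at N = 400 and 80% power, for R = 50, 60, 70, 80 and 90%:

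| Event fraction | 50% | 60% | 70% | 80% | 90% |
|---|---|---|---|---|---|
| Table 3 | 0.67 | 0.69 | 0.71 | 0.73 | 0.74 |
| R in both arms, Freedman | 0.669 | 0.694 | 0.713 | 0.729 | 0.743 |
| R in both arms, Schoenfeld | 0.673 | 0.697 | 0.715 | 0.731 | 0.744 |
| 0.95R, Schoenfeld | 0.666 | 0.690 | 0.709 | 0.725 | 0.739 |
| Average of the two arms, Schoenfeld | 0.653 | 0.681 | 0.704 | 0.723 | 0.739 |

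With R in both arms, Freedman's formula matches every tabulated HR to two decimals and Schoenfeld's is within 0.01. The arm average misses the first four rows. A one-sided 0.05 test (0.687–0.765 with averaged risks, 0.704–0.769 with R in both arms) misses every row.

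**4. Power with each arm's own risk.** Events = 200 × (R + R₂); power = Φ(√events / 2 × |ln HR| − 1.96). For row 1: events = 200 × (0.500 + 0.371) = 174.3, and power = Φ(2.644 − 1.96) = 75.3%.

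| R | HR | Events | Power | Simulated log-rank, 20,000 runs |
|---|---|---|---|---|
| 50% | 0.67 | 174.3 | 75.3% | 74.9% |
| 60% | 0.69 | 213.7 | 77.4% | 77.1% |
| 70% | 0.71 | 254.9 | 78.1% | 77.7% |
| 80% | 0.73 | 298.2 | 77.6% | 77.6% |
| 90% | 0.74 | 343.6 | 79.7% | 79.7% |

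Putting R in both arms instead gives 80.8%, 82.0%, 81.7%, 80.4% and 81.5%.

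**5. Power for exactly 13 points.** The HR is ln(1 − R + 0.13) / ln(1 − R), and events = 200 × (2R − 0.13).

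| R | HR | Events | Power |
|---|---|---|---|
| 50% | 0.667 | 174 | 76.3% |
| 60% | 0.693 | 214 | 76.5% |
| 62% (pilot) | 0.696 | 222 | 77.1% |
| 70% | 0.701 | 254 | 80.8% |

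**6. What N = 400 detects with 80% power.** HR 0.653, 0.681, 0.704, 0.723 and 0.739, which are differences of 13.6, 13.6, 12.9, 11.3 and 8.2 points for R = 50% to 90%.

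**7. Sensitivity to loss.** The documents give no figure. If 10% of events were missed (an assumption), power for 13 points would be about 72% at R = 50%, 72% at 60% and 77% at 70%.

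**The case against.** The authors' computation is not shown, so the cause is inferred from fit, and the fit is imperfect. With R in both arms, even Freedman's version gives a DR of 12.4 points at R = 70% (printed 13) and 8.1 at 90% (printed 8.3). An event fraction of 0.95R fits the HR, DR and RDR columns better, and an unstated 5% allowance could explain it. This stands as a limit on the cause: the table comes close to using R in both arms, and no more can be said. It does not remove the shortfall, which follows from the table's own columns by standard log-rank arithmetic. Nor does the result depend on the cited sample-size paper, which could not be consulted.

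Rounding also matters. With the most favourable unrounded HR (0.665, 0.685, 0.705), power rises to 76.7%, 78.9% and 79.6% for R = 50%, 60% and 70%. That narrows the gap at 60% and 70% but does not close it in any of the three rows. At R = 90% the printed columns together are compatible with 80%, so that row is not at issue.

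The error is small: at most about 0.6 points in the detectable difference, and none at R = 70%, where the 13-point sentence is true. A detectable difference just under 13.5 points would still round to 13%, and at the pilot rate 13.49 points does have 80.0% power. Uncertainty about the readmission rate itself, which the plan admits, is larger than a shortfall of 2 to 5 points in power. All this is fair and limits the weight of the point, but a reader will take 13% as 13 points.

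The 50% mortality assumption does not visibly enter the figures. If R is a cumulative incidence with death competing, it need not, so nothing here rests on it.

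**Conclusion.** The concern holds. At the tabulated hazard ratios, 400 participants give 75.3%, 77.4% and 78.1% power for usual-care readmission of 50%, 60% and 70%, not 80%. For exactly 13 points the stated 80% is reached near 70% readmission but not at 50%, 60% or the 62% pilot rate, where power is 76% to 77%.

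This rests on two-sided testing at 0.05, equal allocation, no loss, and the HR read as acting on cumulative incidence, which the DR column supports. If the test were one-sided, power at these three HRs would be 84–86%, but a one-sided test does not reproduce the table. The shortfall is clearest at 50% and modest throughout. It should be corrected because it is the primary justification for the sample size and errs in the favourable direction.

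**What to change.** Recompute Table 3 with the average event fraction of the two arms, (R + 1 − (1 − R)^HR) / 2, and state that fraction, the sidedness of the test and any allowance for loss. By the calculation above, the HR column becomes 0.65, 0.68, 0.70, 0.72 and 0.74, and the DR column 13.6, 13.6, 12.9, 11.3 and 8.2 points.

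Restate the conclusion in Sections 5.0 and 8.0: before any loss, N = 400 gives about 76% power for a 13-point reduction when usual-care readmission is 50–60%, and about 81% at 70%. At 50–60%, 80% power needs a reduction of about 13.6 points (HR 0.65 to 0.68).

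The cost is a few restated figures, slightly less favourable than the present ones. Sample size, design and analysis stay as they are. For reference, keeping 80% power for exactly 13 points would take about 439 participants at R = 50% (191 events / 0.435) and 436 at R = 60% (233 events / 0.535).
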